Consent will occur in either the patient's hospital room or with family in a consultation room, or in the pre-anesthesia area. Privacy is ensured by curtains or closing doors when available. The study will be discussed with the patient or LAR if the patient is unable to consent. Adequate time will be provided for the patient/LAR to consider participation. No pressure to participate will be introduced. If the patient or LAR wants additional time to consider participation that would delay the surgery, the patient will be excluded so as not to delay standard care. The initial consent is the only time that participation is required, ongoing consent will be maintained with adequate and on-going conversations with the patient/LAR and the research team. The patient or LAR will be asked to describe what is involved in the study to ensure adequate understanding of the study. HIPAA consent will be included in the consent process.

Subjects not fluent in English

N/A

Cognitively Impaired Adults/Adults Unable to Consent/Use of a Legally Authorized Representative

cSDH is a slowly progressive bleed, which may cause altered mental status. Therefore, the physician might not be able to determine the exact time of onset. In this case, any patient with cSDH who is cognitively impaired for more than 6 months, will be excluded from the study; since this impairment might be due to other reasons such as dementia or cognitive impairment. If patients are cognitively impaired and unable to give their own consent to participate in the study due to their cerebrovascular accident; in this case, investigators will identify a LAR and because the patient is not thought to be able to consent for the operation, then the same party consenting for the surgical procedure (if applicable) will be used for consent for the study. All reasonable attempts will be made to ensure that this party is the LAR by asking and ensuring that the same party making medical decisions is making the decision whether to participate in the study. The treating physician will make this determination at the time of consenting the patient for surgery.

It will be explained to the patient/LAR that they have the right to refuse to take part and/or withdraw from this study at any time without penalty or loss of care. Their ongoing medical care will not be affected by the decision to take part or not take part in this study. Patients who decline to take part in this study will receive the standard of care treatment.

m. Documentation of Consent

Consent for the study will be obtained by one of the members of the Department of Neurosurgery clinical research coordinators or one of the investigators. The UNM HSC consent generator will be used.

n. Study Test Results/Incidental Findings

All study subjects will be followed in the outpatient neurosurgery clinic. During the clinic visit, the patients can be shown any of their CT scans, and the progression that has been made. This is currently the practice for all subdural patients. If the patient requires an additional surgical procedure if they underwent an initial craniotomy, or a surgical procedure after initially being managed conservatively, this information will be shared with the patient to allow proper consent for surgery and all of the additionally required steps.

o. Sharing Study Progress or Results with Subjects

No results will be shared with the subjects.

p. Inclusion of Vulnerable Populations

Patients enrolled in the study may be cognitively impaired and unable to provide informed consent; in this case, a legally authorized representative (LAR) will be appropriately identified and approached by a research coordinator to provide consent. These discussions will take place in a private setting where privacy and confidentiality can be maintained. It will be explained appropriately to the LAR that they have the right to refuse participation in the study and/or withdraw at any time without penalty or loss of care.

q. Community-Based Participatory Research

N/A

r. Research Involving American Indian/Native Populations

N/A

s. Transnational Research

N/A

t. Drugs or Devices

A. Turmeric pills to be used:

Wild harvest: Serving size: 3 capsules

Composition: 95% curcuminoids in 825 mg = 784 mg curcumin

5% curcuminoids in 525 mg = 26 mg

Pepperine: 9 mg

Each capsule contains: **~270 mg of pure curcuminoids and 3 mg of black pepper extract.**

Turmeric/pepperine extracts are in the vegetarian cellulose capsules with the same composition as placebo capsules

- The dose is chosen based on other clinical studies as well as the manufacturer's recommended dosage.
- If you refer to the in-vitro studies on cells, the curcumin concentration is based on the available scientific literature

B. Placebo pills: The placebo pill is a vegetarian cellulose capsule, with cellulose powder inside. The composition is cellulose and magnesium stearate. Produced by MHS Labs. Certificate of Manufacture provided.

Turmeric and placebo pills will be stored (at room temperature) and sorted in the standard pill bottles in the UNM Hospital Pharmacy.

For blinding purposes, both types of capsules (Turmeric and placebo) will be over-encapsulated in an empty, opaque, orange gelatin capsule shell.

Checklist Section

This section contains checklists to provide information on a variety of topics that require special determinations by the IRB. Please complete all checklists relevant to your research.

I. Waivers or Alterations of Consent, Assent, and HIPAA Authorization

A. Partial Waiver of Consent for Screening/Recruitment

Complete this checklist if you are requesting a partial waiver of consent so that you can review private information to identify potential subjects and/or determine eligibility prior to approaching potential subjects for consent or parental permission.

1. Describe the data source that you need to review (e.g., medical records):
2. Describe the purpose for the review (e.g., screening):
3. Describe who will conducting the reviews (e.g., investigators, research staff):
4. Do all persons who will be conducting the reviews already have permitted access to the data source?
 Yes
 No. Explain:
5. Verify that each of the following are true or provide an alternate justification for the underlined regulatory criteria:
 - a) The activity involves no more than minimal risk to the subjects because the records review itself is non-invasive and the results of the records review will not be used for any purposes other than those described above.
 True
 Other justification:
 - b) The waiver or alteration will not adversely affect the rights and welfare of the subjects because eligible subjects will be approached for consent to participate in the research and are free to decline. Further, the information accessed during the records review will not be disclosed to anyone without a legitimate purpose (e.g., verification of eligibility).
 True
 Other justification:

c) The research could not practicably be carried out without the waiver or alteration because there is no other reasonably efficient and effective way to identify who to approach for possible participation in the research.

True
 Other justification:

d) Whenever appropriate, potentially eligible subjects will be presented with information about the research and asked to consider participation.
(Regulatory criteria: Whenever appropriate, the subjects will be provided with additional pertinent information after participation.)

True
 Other justification:

Partial Waiver of HIPAA Authorization for Screening/Recruitment

Complete the following additional questions/attestations if the records you will review to identify potential subjects and/or determine eligibility include Protected Health Information (PHI).

6. Will you be recording any PHI when conducting the records review to identify potential subjects and/or determine eligibility?

Yes. Describe:

No

7. If you answered "Yes" to question 6 above, please describe when you will destroy identifiers (must be the earliest opportunity consistent with the conduct of the research) or provide justification for why they must be retained:

The use of PHI for screening involves no more than minimal risk, as we already have access to this information for clinical care of these patients. PHI that may be used/viewed for screening will not be retained in any way after the consent process has been completed. If the patient is determined to not be an eligible participant or declines consent, all PHI that may have been collected during screening will be destroyed immediately and will not be retained in any way. If the patient is determined to be eligible, the patient will be consented and will sign a HIPAA authorization at that time. Any PHI collected for screening purposes will be destroyed at the earliest time possible and will not be disclosed or re-used.

8. The PHI accessed or recorded for identification/screening purposes will not be reused or disclosed to (shared with) any other person or entity, except as required by law, for authorized oversight of the research study, or for other research for which the use or disclosure of the PHI would be permitted under the Privacy Rule.

True

False

B. Waiver of Documentation of Consent

Complete this checklist if you intend to obtain consent verbally but will not be obtaining signatures from subjects on a consent form to document consent. Waivers of documentation of consent are commonly requested when using scripts, information sheets, or email or survey introductions to present the elements of consent instead of using a traditional consent form.

1. Are you requesting a waiver of documentation of consent for some or all subjects?
 All
 Some. Explain:
2. Provide justification for one of the following:
 - a) That the only record linking the subject and the research would be the consent document and the principal risk would be potential harm resulting from a breach of confidentiality. Each subject will be asked whether the subject wants documentation linking the subject with the research, and the subject's wishes will govern.
 - b) That the research presents no more than minimal risk of harm to subjects and involves no procedures for which written consent is normally required outside of the research context.
3. Do you intend to provide subjects with a written statement regarding the research in lieu of a traditional consent form?
 Yes. Please attach a copy to your submission in Click.
 No

C. Alteration of Consent

Complete this checklist if you intend to obtain consent but will be eliminating or altering one or more of the required elements of consent. Alterations of consent are commonly requested for research involving deception or for minimal risk research when an abbreviated consent is desired and one or more of the required element are not relevant to the research.

Note: FDA-regulated research is not eligible for an alteration of consent.

1. Which element(s) of consent do you wish to eliminate and why?
2. Which element(s) of consent do you wish to alter and why?

3. Provide justification for each of the following regulatory criteria:
 - a) The research involves no more than minimal risk to the subjects:
 - b) The waiver or alteration will not adversely affect the rights and welfare of the subjects:
 - c) The research could not practicably be carried out without the waiver or alteration:
 - d) Whenever appropriate, the subjects will be provided with additional pertinent information after participation:

D. Full Waiver of Consent/Parental Permission

Complete this checklist if you are requesting a full waiver of consent for all subjects or certain subject groups (e.g., retrospective cohort). Full waivers of consent are commonly requested when the research does not include any opportunity for interaction with subjects (e.g., chart review).

Note: FDA-regulated research is not eligible for a full waiver of consent using these criteria.
If you believe that your FDA-regulated research may be eligible for a waiver under another mechanism, such as planned emergency research, contact the HRPO for assistance in determining what information to provide to the HRRC.

1. Are you requesting a waiver for some or all subjects?
 All
 Some. Explain:
2. Provide justification for each of the following regulatory criteria:
 - a) The research involves no more than minimal risk to the subjects:
 - b) The waiver or alteration will not adversely affect the rights and welfare of the subjects:
 - c) The research could not practicably be carried out without the waiver or alteration:

d) Whenever appropriate, the subjects will be provided with additional pertinent information after participation:

E. Full Waiver of Consent/Parental Permission (Public Benefit or Service Programs)

Complete this checklist if you are requesting a full waiver of consent for all subjects or certain subject groups (e.g., retrospective cohort) and the research involves the evaluation of a public benefit or service program.

1. Are you requesting a waiver for some or all subjects?

All

Some. Explain:

2. Provide justification for each of the following regulatory criteria:

a) The research or demonstration project is to be conducted by or subject to the approval of state or local government officials and is designed to study, evaluate, or otherwise examine: (i) public benefit or service programs; (ii) procedures for obtaining benefits or services under those programs; (iii) possible changes in or alternatives to those programs or procedures; or (iv) possible changes in methods or levels of payment for benefits or services under those programs:

b) The research could not practicably be carried out without the waiver or alteration.

F. Full Waiver of HIPAA Authorization

Complete this checklist if you are requesting a full waiver of the requirement to obtain HIPAA authorization for all subjects or certain subject groups (e.g., retrospective cohort). Full waivers of HIPAA authorization are commonly requested when the research does not include any opportunity for interaction with subjects (e.g., chart review).

1. Are you requesting a waiver of authorization for some or all subjects?

All

Some. Explain:

2. Describe your plan to protect health information identifiers from improper use and disclosure:

3. Describe your plan to destroy identifiers at the earliest opportunity consistent with conduct of the research (absent a health or research justification for retaining them or a legal requirement to do so):
4. Describe why the research could not practicably be conducted without the waiver or alteration:
5. The PHI accessed or recorded for identification/screening purposes will not be reused or disclosed to (shared with) any other person or entity, except as required by law, for authorized oversight of the research study, or for other research for which the use or disclosure of the PHI would be permitted under the Privacy Rule.
 True
 False

G. Other Waiver Types

If you are seeking another waiver type (e.g., Planned Emergency Research, Waiver of Parental Permission to Protect Child Participants, Enforcement Discretion for In Vitro Diagnostics, etc. contact the HRPO office for assistance in determining what information to submit for the HRRC's consideration.

II. Vulnerable Populations

A. Adults with Cognitive Impairments

Complete this checklist if the subject population will include adults with cognitive impairments.

This checklist does not need to be completed if the research doesn't involve interactions or interventions with subjects and will be conducted under a waiver of consent.

1. Describe why the objectives of the study cannot be met without inclusion of adults with cognitive impairments.

cSDH is a slowly progressive bleed, which may cause altered mental status. Therefore, the physician might not be able to determine the exact time of onset. In this case, any patient with a cSDH, who is cognitively impaired for more than 6 months, will be

excluded from the study; since this impairment might be due to other reasons such as dementia or cognitive impairment.

2. Describe how capacity to consent will be evaluated.

Again, due to the nature of the injury, some patients will be unable to consent for themselves. If the patient is not thought to be able to consent for the trial, then the same party consenting for the surgical procedure will be used for consent for the study. All reasonable attempts will be made to ensure that this party is the LAR by asking and ensuring that the same party making medical decisions is making the decision whether to participate in the study. The treating physician will make this determination at the time of consenting the patient for the surgical procedure.

3. If subjects may regain capacity to consent, or if subjects may have fluctuating capacity to consent, describe your plans to evaluate capacity to consent throughout the research and to obtain consent to continue participation if capacity is regained.

If the patient regains the ability to provide informed consent (i.e. above GCS 13), the study will be explained to them, and they will be asked to decide on their further participation. Patients are assessed daily for competence by the resident and attending neurosurgeon. This assessment will include a basic assessment of orientation as well as using the “repeat back” method (Cordasco Making Health Care Safer II: An Updated Critical Analysis of the Evidence for Patient Safety Practices. Chapter 39, 2013) to assess whether the subject is competent to make a determination.

4. Describe your plans, if any, to provide information about the research to subjects and the steps you will take to assess understanding.

During consent of the subject/LAR, we will use the teach back method to ensure understanding of all study related procedures. This method will be done with the participant, if the participant regains consciousness and is determined to be able to consent by the attending physician.

5. Describe your plans to obtain assent, including whether assent will be obtained from none, some, or all subjects.

Assent will not be obtained.

Describe why risks to subjects are reasonable in relation to anticipated benefits to the subjects.

The risks to the study subjects are minimal, as the study drug curcumin (CC) is an active ingredient in the popular cooking spice turmeric. Also, the management and follow-up of these patients is the same as the standard of care for all SDH patients seen by the UNM Neurosurgery department.

6. If this study involves a health or behavioral intervention, describe why the relation of the anticipated benefit to the risk of the research is at least as favorable to the subjects as that presented by alternative procedures.

Title: Clinical Action of Curcumin/Turmeric In chronic Subdural hematoma recurrence (CACTIS)

Since there is no treatment for patients, with recurrent cSDH, other than the Standard of Care, we believe that Curcumin will be very effective in reducing the recurrence of previously evacuated chronic subdural hematomas.

7. Describe your plans for monitoring the well-being of subjects including any plans to withdraw subjects from the research if they appear to be unduly distressed.

Please see protocol in section 15.

References:

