3.2.2 Exclusion criteria

- Age < 18 years old
- Bilateral subdural hematomas
- Subdural volume $< 115\text{cc}$
- Acute subdural hematoma
- Patient does not undergo surgical evacuation
- Other evidence of intracranial injury (i.e. epidural hematoma, intraparenchymal hemorrhage, skull fractures, subarachnoid hemorrhage, hydrocephalus)
- Patient's family not available for consent and requires emergent surgical evacuation
- Previous intracranial surgery
- Recent head trauma (< 1 week)

Title: Clinical Action of Curcumin/Turmeric In chronic Subdural hematoma recurrence (CACTIS)

- Use of anti-coagulation (i.e. Coumadin, Heparin, Apixaban, and Rivaroxaban) or anti-platelets (Plavix) drugs, with the exception of Aspirin
- Known coagulopathy disorders
- Positive urine or serum pregnancy test in pre-menopausal female subjects, without a documented history of surgical sterilization; or currently breastfeeding

1.1.1.□.1. Since the nuclear group in an older population, the pregnancy test will be made in exceptional cases.

- Allergy to curcumin or turmeric.
- Allergy to black pepper
- Markwalder Grading Scale

1.1.1.□.1. Score: 3-4

- Baseline dementia (for more than 6 months).
 - Adult who cognitively impaired for more than 6 months will be excluded from the study, since this impairment might be due to other reasons than cSDH, such as dementia or cognitive impairment.

4. Number of Subjects

This is a single center pilot study. A total of 48 subjects will be recruited in this study.

24 patients will receive placebo pills, and 24 will receive Curcumin (CC) pills. Patients will be first stratified according to their pre-surgery hematoma volume. Randomization will be performed within each hematoma volume group (12 subjects per hematoma volume group) to ensure equal distribution between placebo and CC groups.

Study Timelines

- Duration of an individual subject's participation in taking CC or placebo will be for up to a maximum of 60 days, with follow-up at 6 months and 18 months
- Clinical follow-up with CT scans will be up to 6 months, depending on if residual total hematoma volume < 80cc
- Enrollment of subjects will continue for 2 years.
- Complete data analysis will be performed within 2 years.

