cSDH patients will take one capsule three times a day for up to 60 days. Because maximum treatment duration is 60 days, IDS will dispense a total of 180 capsules. IDS will dispense this amount on two occasions to reduce waste and save cost for cases in which treatment may end early. They will undergo standard post-operative care in regard to imaging and clinical follow-up.

- Patients will begin taking placebo or CC within 24 hours post-operatively and able to take oral medication. It will then be continued TID.
- CT Imaging:
 - Pre-operative CT SOC scan
 - If the hematoma volume is < 115 cc, the patient will not be included in the study
 - Post-operative day one CT SOC scan within 24 hours of surgery.
 - Post subdural drain removal SOC scan usually 1-2 days after surgery.

Title: Clinical Action of Curcumin/Turmeric In chronic Subdural hematoma recurrence (CACTIS)

- If the residual total hematoma cavity volume is $<80\text{cc}$, the patient will be dropped from study, as the curcumin has not had time to influence the patient's reabsorption.
- *During the SOC one week follow-up appointment without a CT scan*, the attending will decide on the need for a repeat CT scan in 4 weeks based on the patient's **post-subdural drain removal SOC scan**.
 - If the residual total hematoma cavity volume is $\geq 80\text{cc}$, the patient will receive an additional CT scan (SOC) for an appointment one month following the previous appointment (Approximately post-operative day 37)
 - If there is a decline in neurological exam or other clinical concern, the neurosurgeon may perform an earlier CT scan
- This will continue on a monthly basis for 6 months, or until residual total hematoma cavity volume is $< 80\text{cc}$
 - **Resolution** will be defined as residual total hematoma cavity volume $< 80\text{cc}$
 - Patients with resolution of their hemorrhage will no longer require Tx or follow-up visits. Their pills will be returned and discarded. These patients will receive phone **call** follow-ups at 1-month, 6-month, and 18-month intervals

All radiographic imaging discussed here is our institution's standard of care for the management of SDH. If Tx discontinued, the patients will still be followed according to the schedule below

- Study Follow-Up **Phone Calls**
 - 1 month, 6 months, 18 months
 - Modified Ranking Scale (MRS) (Appendix 3)
 - Markwalder Grading Scale (Appendix 4)

5. Study Endpoints

5.1. Describe the primary and secondary study endpoints.

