Patients who have symptomatic unilateral chronic subdural hematomas, with no acute component and do not meet the exclusion criteria, will be evaluated. At the time of consent for evacuation of the subdural hematoma, patients will also be consented for this trial by the research team. They will be instructed that they will be randomized to either the placebo group or the curcumin group. They will take one capsule three times a day for a maximum of 60 days. They will undergo standard post-operative care in regard to imaging and clinical follow-up.

Evaluation:

1. Patient evaluated by neurosurgery resident

Title: Clinical Action of Curcumin/Turmeric In chronic Subdural hematoma recurrence (CACTIS)

2. Patient or POA consented by Neurosurgery resident for cSDH evacuation in the operating room.
3. Evaluated by research team for inclusion into trial within 48 hours of presentation to the Neurosurgery service
4. Consent patient or POA for trial participation

Interventions:

1. *Intra-operatively*, patient has samples sent to lab
 - a. At least 10 cc of subdural hematoma fluid will be collected during the initial and recurrence operative, along with 5 cc blood from an existing IV
 - b. The SDH fluid and blood samples will be sent to [name] lab and used in the experimental setup within 10-15 days of collection and in addition analyzed for inflammatory cytokines/chemokines.
2. *Presurgical randomization by stratified hematoma volume.* Presurgical hematoma volume randomization is important because recurrence of cSDH has been shown to be related to presurgical hematoma volume by Stanisic et al.³⁷ The hematoma volume and other CT characteristics are recorded as shown in **Table 1** below.
 - a. Hematoma volume will be recorded and stratified into two groups according to hematoma volume: >140 ml and \leq 140 ml. The process of stratification and subsequent randomization will be done by the IDS pharmacist who will conceal the randomization results from all study team members until after the results of the study have been analyzed.
 - b. After the first patient is consented, we will record his or her hematoma cavity volume. All subjects will be assigned to a treatment group to receive either curcumin-containing or non-curcumin-containing capsules.

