 - c. For the next patient, we will first determine the hematoma cavity volume group; this patient's Tx assignment (CC or placebo) will be alternate to the immediately preceding patient. This process is repeated until all of the patients are enrolled.
3. The patients will start medication **within 24 hours after surgery**, or as soon as they are able to take oral medication
 - a. 1 capsule three times a day (with breakfast, lunch, and dinner) for a maximum of 60 days or until resolution of subdural hematoma
 - b. Resolution will be defined as residual total hematoma cavity volume $<$ 80cc
 - i. If the post-subdural drain removal scan demonstrates a residual total hematoma volume $<$ 80cc, the patient will not be included in the study sample; although, the patient may receive more than one dose of CC by the time of the CT scan.

- CT Imaging:
 - Pre-operative CT SOC scan-- If the hematoma volume is $<$ 115 cc, the patient will not be included in the study
 - Post-operative day one CT SOC scan
 - Post subdural drain removal SOC scan--If the residual total hematoma cavity volume is $<$ 80cc, the patient will be removed from study, as the curcumin has not had time to influence the patient's reabsorption.
 - During the SOC 1 week follow-up appointment, the attending will decide on the need for a repeat CT scan in 4 weeks based on the patient's **post-subdural drain removal SOC scan**. The considerations for re-evacuation include: lack of resolution of the initial clot, an obvious increase in size of the clot, persistent headache, onset of seizures, or onset of new deficit or headache. These criteria will be used in all subsequent considerations for surgical re-evacuation.

Title: Clinical Action of Curcumin/Turmeric In chronic Subdural hematoma recurrence (CACTIS)

- If the residual total hematoma volume is $\geq 80\text{cc}$, the patient will receive an additional CT scan (SOC) for an appointment one month following the previous appointment (Approximately post-operative day 37)
- If there is a decline in neurological exam or other clinical concern, the neurosurgeon may perform an earlier CT scan
- This will continue on a monthly basis for 6 months, or until residual total hematoma cavity volume is $< 80\text{cc}$
 - **Resolution** will be defined as residual total hematoma cavity volume $< 80\text{cc}$
 - Patients with resolution of their hemorrhage will no longer require follow-up visits. Their pills will be returned and discarded.

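### The residual-cavity test (at least 80cc) comes after allocation and possibly after dosing, so 24 analysed per arm and balance within volume strata are not assured

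*Combined protocol and SAP*

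**What the plan says.** The order of events has to be pieced together from section 4 (Number of Subjects, with Study Timelines) and section 9 (Study Procedures).

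- **Allocation.** Interventions item 2 is headed "Presurgical randomization by stratified hematoma volume". The investigational pharmacy allocates within two pre-operative volume strata, above 140 ml and at or below 140 ml.
- **First dose.** Capsules, three a day, start within 24 hours after surgery, "or as soon as they are able to take oral medication".
- **Last eligibility test.** The scan after drain removal is usually done 1-2 days after surgery. Under Study Timelines, a patient whose residual cavity is below 80cc on that scan leaves: "the patient will be dropped from study, as the curcumin has not had time to influence" reabsorption. Of the same patient, Interventions item 3.b.i says: "the patient will not be included in the study sample; although, the patient may receive more than one dose of CC". The doses meant are those taken before this scan. This rule is not among the criteria in section 3.2, which tests only the pre-operative volume (at least 115cc).
- **Numbers.** Section 4 states: "A total of 48 subjects will be recruited in this study". It assigns 24 to each arm and randomizes within volume groups "to ensure equal distribution between placebo and CC groups".

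No expected removal share, allowance or replacement rule is given, and no analysis set is defined for patients who were dosed and then removed.

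**The concern.** When eligibility is settled after allocation, the allocation scheme no longer controls who is analysed. Here the scheme aims at 24 per arm, balanced within volume strata, but removal at the 80cc test falls by chance across arms and strata. What remains need be neither 24 per arm nor balanced.

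The plan also does not say what the 48 counts. The word recruited in section 4 suggests everyone allocated. Leaving removed patients out of the study sample (item 3.b.i), together with item 2.c, "This process is repeated until all of the patients are enrolled", can be read as meaning only those kept. The first reading costs precision. The second means more patients allocated than the plan states. On both, some patients who fail the last test have already taken capsules. The pilot is meant to assess feasibility and to estimate an effect with confidence intervals, so the evaluable number matters to its purpose.

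**Working it through.** **The plan's own figures.** Section 4: 24 + 24 = 48. The Statistical analysis section instead gives 25 per group, or 50; that mismatch is a separate point. Its statement about 80% power cannot be reproduced, because the control rate, alpha, sidedness and scale of the 50% (points or ratio) are not given. At two-sided 0.05 and 25 per arm, a gain of 50 points gives about 97-99% power, while 1.5 times a control rate of 0.50 gives about 44%. Neither section shows an allowance for removals. I therefore use confidence-interval width, which needs none of the missing inputs.

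**Timing.** With a first dose at 24 hours and a scan at day 2, a patient on three capsules a day may have taken about three. Item 3.b.i says only that more than one dose may be received, so the frequency is unknown.

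**Size.** Let q be the share removed. The documents do not give it; 10%, 25% and 50% are assumptions.

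- If the 48 counts everyone allocated: evaluable = 48(1 - q), and interval width is multiplied by 1/√(1 - q).
- If the 48 counts only those kept: allocations needed = 48/(1 - q).

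| q (assumed) | Evaluable of 48 | Width factor | Allocations for 48 kept |
|---|---|---|---|
| 10% | 43.2 | 1.054 | 53.3 |
| 25% | 36 | 1.155 | 64 |
| 50% | 24 | 1.414 | 96 |

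**Example on the plan's 75% interval.** Assume 50% resolution in both arms. The half-width for a difference is 1.150 × √(2 × 0.25/n), with n per arm. For n = 24 it is 16.6 points. For n = 21.6, 18 and 12 (the three values of q) it is 17.5, 19.2 and 23.5 points.

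**Balance, only if the 48 counts everyone allocated.** Read section 4's 12 subjects per group as 12 per arm per stratum (4 × 12 = 48). The number kept in each cell is then Binomial(12, 1 - q). The two arms within a stratum differ by 3 or more with probability 8%, 23% or 31%. The average efficiency, 4n₁n₂/(n₁ + n₂)², is 0.995, 0.985 or 0.952, so the precision lost through imbalance alone is small. These figures do not carry over to the case where removed patients are replaced.

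**The case against.** The strongest case for the plan is that the rule is disclosed and reasoned. It uses a CT volume threshold, applied while patients, surgeons, nurses and coordinators are masked. A patient below 80cc already meets the plan's definition of resolution, so cannot inform time to resolution. The study is a pilot sized by logistics. All of this stands, and it keeps the point modest. It does not restore 24 analysed per arm or undo exposure of patients who fail the test.

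The one-week clinic visit raises a practical objection. Clinic Follow-up, item 2, has the volume from the last scan measured at that visit, and patients below 80cc told then to stop. Allocating after the scan would thus delay treatment by up to about a week unless the scan is read earlier. The objection is right, and the fix has to require an in-hospital reading. It also means that exposure before removal could last about a week if the volume is not read sooner.

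A reader might infer more than the documents support:

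- **Biased comparison.** Removal is masked, and the plan holds that curcumin has had no time to act by that scan. Little bias is expected.
- **Enrolment running past two years.** Section 4 says "Enrollment of subjects will continue for 2 years" but gives no accrual rate. A pace of 24 a year presumes that the 48 already includes removed patients, so it cannot be used to time the case where it does not. No delay can be derived.
- **Removed patients contributing nothing.** Patients no longer in the study are called at 1, 6 and 18 months, and the tolerability endpoint (5.2.1) does not exclude them. What is missing is a defined analysis set.
- **Balance otherwise guaranteed.** Item 2.c alternates from the preceding patient without saying whether this is within stratum, so balance may not be assured even without removals.

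**Conclusion.** The point holds and should be fixed. The last eligibility test follows allocation and may follow dosing. As written, the plan assures neither 24 analysed per arm nor the within-stratum balance it seeks, and it exposes some ineligible patients.

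The size depends on a removal share that the plan does not give. Over an assumed 10% to 50%, intervals are 5% to 41% wider if the 48 includes removed patients, or about 53 to 96 allocations are needed if it does not. The upper figures rest wholly on the 50% assumption. No loss of power is claimed, because the plan's power statement lacks the inputs to compute one. Harm to validity is expected to be small, provided masking holds and 1-2 days of capsules do not change the cavity. The case for acting is that the problem can be avoided with scans already taken.

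**What to change.** Amend the protocol as follows.

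1. Read the total residual cavity volume in hospital on the post-drain scan, or on the post-operative day-one scan if no drain was placed, rather than leaving it to the one-week visit. Table 1 already records this volume for both scans.
2. Have the investigational pharmacy allocate within pre-operative volume stratum, and start capsules, only once at least 80cc is confirmed.
3. Count the 48 from those allocated, and list the 80cc rule among the eligibility criteria in section 3.2.

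Cost: an amendment to intervention timing, a prompt volume reading, and a first dose about 1-2 days later in a course of up to 60 days. The plan already lets the start wait for oral intake. Both scans are standard of care, so no scan or visit is added.

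If the 24-hour start is kept, state whether the 48 includes removed patients, report removals below 80cc by arm, and keep every dosed patient in the tolerability analysis. That is a text change only; it makes the removals visible but does not prevent them.
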